ANALYTIC PLAN FOR PROTOCOL A Pilot Study of Hypertension Management Using Remote Patient Monitoring Study 1

PRINCIPAL INVESTIGATOR:

[name], MPH
Professor of Medicine, Division of General Internal Medicine & Geriatrics
Director, Center for Primary Care Innovation
[contact]
Email Address: [contact]

VERSION DATE: 1/26/21

Start date 11/19/2020

Define primary study cohort as of this date

Define secondary study cohort as of this date

Define matched control cohort as of this date (attempt to match pilot to control at rate of 4:1 for primary and 2:1 for secondary)

Groups of interest:

- Patients meeting **primary patient population** criteria at the study start date
 - Adults aged 65 to 85 years at the time of the study start date AND
 - One or more office or telehealth visits in the year preceding the study start date at the eligible NM primary care sites AND
 - Medicare or Medicare Advantage insurance on study start date AND
 - Last two office blood pressures elevated (either ≥ 140 mmHg systolic or ≥ 90 mmHg diastolic) in the past 2 years AND
 - Diagnosis of hypertension in the year preceding the study start date (problem list or encounter diagnosis : all of the subcodes of I10, I11, I12, I13, I15) AND
 - Not meet the exclusion criteria
 - Persistent atrial fibrillation as indicated in the EHR
 - Exclude if “permanent atrial fibrillation or persistent atrial fibrillation” [I48.1, I48.2] (active problem list or two encounter diagnoses in past 2 years)
 - Stage IV or more severe kidney disease, defined as the most recent estimated glomerular filtration rate < 30 per $1.73m^2$ or currently on renal replacement therapy (i.e. hemodialysis or peritoneal dialysis) [N18.4, N18.5, N18.6]
 - Diagnosis of dementia as indicated in the electronic health record [all subcodes of F01-F03, all subcodes of G30, all subcodes of G31]
- Patients meeting **secondary patient population** criteria at the study start date
 - Meet criteria for primary population OR
 - Diagnosed hypertension but did not have the last two office blood pressures ≥ 140 mmHg systolic or ≥ 90 mmHg diastolic OR
 - No diagnosis of hypertension in the past year but did have the last office blood pressure ≥ 140 mmHg systolic or ≥ 90 mmHg diastolic

- Control group matched based on the primary study criteria
- Control group matched based on the secondary study criteria.

Matching criteria

- Sex
- Age (+/- 5 years)
- Mean SBP from T-365d to T-183d (+/- 10 mm Hg)

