- Mean SBP from T-182d to T-0d (+/- 10 mm Hg)
- Number of office visits to primary care in the past year categories : 1, 2, 3-4, 5+

Assess for time 0 (11/19/2020)

Characteristics of study populations and matched control populations.

At time 0, 1 month (12/18/2020), 3 months (2/18/2020) and 6 months (5/18/2020) describe for each group:

- The proportion of patients who satisfy the performance measure Controlling High Blood Pressure (NQF 0018)
- The systolic blood pressure at the most recent face-to-face office visit

At time 1 month (12/18/2020), 3 months (2/18/2020) and 6 months (5/18/2020) describe for each group:

- Number of antihypertensive medication intensifications between the study start and the measure date

Hypothesis testing—perform separately for primary and secondary populations

H1: Antihypertensive medication intensification will be greater in pilot clinic(s) with RPM compared to contemporaneous control clinic(s).

Compare at 1, 3, and 6 months the number of medication intensifications between study group and control group using Poisson regression (if variance of medication intensifications is approximately equal to the mean) or otherwise negative binomial regression with study group as the independent variable.

H2: The proportion of patients who satisfy the performance measure Controlling High Blood Pressure (NQF 0018) will be greater in pilot clinic(s) with RPM compared to contemporaneous control clinic(s).

Compare at 1, 3, and 6 months the proportion of patients in the study group and control group who satisfy the performance measure Controlling High Blood Pressure (NQF 0018) using logistic regression with study group and baseline systolic blood pressure as independent variables.

H3: The systolic blood pressure at the most recent office visit will be lower in pilot clinic(s) with RPM compared to contemporaneous control clinic(s).

Compare at 1, 3, and 6 months the systolic blood pressure at the most recent face-to-face office visit among patients in the study group and control group using linear regression with study group and baseline systolic blood pressure as independent variables.

RPM enrolled patient analyses

We will explore the trajectories of blood pressure for individuals who are prescribed RPM.

We will describe all patients who are enrolled in RPM at their enrollment date and follow their blood pressure outcomes at 1, 3, and 6 months from their enrollment (or until the study end date).

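### H3's follow-up systolic pressure has no earliest date, so a pre-start reading can stand as the 1-, 3- or 6-month outcome; the 3- and 6-month dates also carry the wrong year

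*SAP*

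**What the plan says.** The list of measures for time 0 and for 1, 3 and 6 months includes systolic pressure at the latest face-to-face office visit, in the same words at every time point. The H3 paragraph repeats this as the outcome: "the systolic blood pressure at the most recent face-to-face office visit among patients in the study group and control group". The hypothesis is that this pressure "will be lower in pilot clinic(s) with RPM compared to contemporaneous control clinic(s"), and the model is a linear regression on study group and baseline systolic pressure. No window is given, and there is no rule for a patient who has not been seen since the start.

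The next measure, used for H1, is bounded at both ends: "Number of antihypertensive medication intensifications between the study start and the measure date".

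The start date is 11/19/2020. The measure dates appear in two lists, both reading "1 month (12/18/2020), 3 months (2/18/2020) and 6 months (5/18/2020) describe for each group".

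The matching criteria include "Number of office visits to primary care in the past year categories : 1, 2, 3-4, 5"+ and mean systolic pressure in two consecutive half-year windows, the later of which runs up to and includes day 0: "Mean SBP from T-182d to T-0d (+/- 10 mm Hg"). For entry to the primary population, a telehealth visit in the prior year is enough.

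**The concern.** Because the definition is the same at time 0 and at follow-up, a patient with no face-to-face visit after the start keeps the time-0 value as the outcome. That value may also be the baseline covariate, so adjusting for baseline does not repair it. The 1-month window is only 29 days, and telehealth visits do not update this outcome.

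Two consequences follow. Carried readings pull the H3 difference towards zero, roughly in proportion to the share not re-measured and most strongly at 1 month. In the primary population, which is selected on elevated readings, pressure tends to fall at the next measurement even without treatment. If post-start visit rates differ between pilot and control clinics, this fall is recorded more often in one group, and H3 can be biased either way. Matching on past-year visits balances prior visiting only.

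The comparison of RPM-enrolled patients with matched controls is described as analogous, so it inherits the gap. The descriptive follow-up of enrolled patients, counted from their enrollment, can be read as bounded and is not part of this point.

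The wrong year is a separate, editorial matter. It affects the dates for all three hypotheses, and for H2 nothing else is raised here.

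**Working it through.** **Dates.** Days from 11/19/2020:

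| Date | Day |
|---|---|
| 12/18/2020 (1 month) | +29 |
| 2/18/2020 (3 months, as printed) | −275 |
| 5/18/2020 (6 months, as printed) | −185 |
| 2/18/2021 | +91 |
| 5/18/2021 | +180 |

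Read literally, the 3- and 6-month measures precede the start and the H1 counting interval is negative. With 2021 they fit the labels. Correcting the year does not supply a start bound.

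**Share re-measured (illustration).** The SAP gives no such share. Assume that past-year visit categories continue as rates r of 1, 2, 3.5 and 5 a year, in equal mix and at random times. The share with a visit by day d is the mean over categories of 1 − exp(−r·d/365). At day 29 the four categories give 7.6%, 14.7%, 24.3% and 32.8%, mean 19.8%. The two half-year pressure windows used for matching suggest at least two readings a year, so a second row omits the one-visit category. A third row doubles the rates, in case office readings outside primary care also count.

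| Rates per year | Day 29 | Day 91 | Day 180 |
|---|---|---|---|
| 1, 2, 3.5, 5 | 19.8% | 47.7% | 68.8% |
| 2, 3.5, 5 | 23.9% | 56.2% | 78.8% |
| 4, 7, 10 | 41.6% | 79.1% | 94.1% |

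**Dilution.** H3 compares all eligible pilot-clinic patients with controls, so the effect that matters is the average over all pilot-clinic patients, whether or not they use RPM. Expected H3 difference = true average × share re-measured. For an assumed −5 mmHg:

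| Rates per year | 1 month | 3 months | 6 months |
|---|---|---|---|
| 1, 2, 3.5, 5 | −1.0 | −2.4 | −3.4 |
| 2, 3.5, 5 | −1.2 | −2.8 | −3.9 |
| 4, 7, 10 | −2.1 | −4.0 | −4.7 |

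**Unequal visiting.** This was simulated with 3 million patients before selection, 20% of them in pilot clinics. Assumed systolic pressure: true mean/SD 135/12 with visit-to-visit SD 10, or 138/13 with visit-to-visit SD 13. Assumed diastolic pressure: mean 76, SD 8, visit-to-visit SD 7, correlation 0.6 with systolic. Entry followed the primary-population rule (both last readings elevated). The SAP does not define baseline, so it was taken as the last pre-start reading. The mean change at a new visit was −4.4 to −5.8 mmHg without any treatment effect. Each 10-point gap in visit share therefore shifts H3 by 0.4 to 0.6 mmHg: upwards if pilot patients are seen less, downwards if they are seen more.

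**Is a post-start-only analysis safer?** Assume 40% re-measured in each group, and that visits of RPM users depend on their current pressure (log-odds 0.4–1.0 per 10 mmHg). H3 estimates in mmHg, with −5 in users where an effect is assumed:

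| RPM uptake | True average | Post-start only | Carry-forward |
|---|---|---|---|
| 25% | 0 | +0.3 to +0.9 | +0.1 to +0.2 |
| 50% | 0 | +0.6 to +1.8 | +0.1 to +0.4 |
| 100% | 0 | +1.1 to +3.6 | +0.2 to +0.8 |
| 25% | −1.25 | −0.4 to −1.0 | −0.3 to −0.5 |
| 50% | −2.5 | −0.7 to −2.0 | −0.6 to −0.9 |
| 100% | −5 | −1.4 to −3.9 | −1.3 to −1.8 |

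Post-start-only has the larger bias with no effect. With an effect it is mostly nearer the truth, but still too small.

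**The case against.** The strongest reply is that the latest available reading may be a deliberate choice. It keeps the whole matched cohort and the matched sets, and in the selection scenario above it has the smaller bias when there is no effect. On this view the plan faces a trade-off between two imperfect estimands. That stands, and it is why the remedy does not replace the written version.

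The definition could also be read as meaning a follow-up reading, since baseline pressure is a separate covariate, and the protocol, which was not available for this review, may set a window. But the SAP itself defines this outcome and bounds its neighbour for H1, so the literal reading is unbounded. If two readings are possible, the text still needs to settle which applies.

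The sizes rest on assumed rates. Patients with uncontrolled pressure may return sooner than at random, and at 6 months the dilution could be as small as about 6% (100 − 94.1) or as large as about 31% (100 − 68.8). The loss of power is also smaller than the dilution suggests. Carried readings equal the baseline covariate, if baseline is the last pre-start reading, so residual variance shrinks too. A simulation with visits independent of pressure gave carry-forward test statistics of 81–83% of the post-start-only ones at 20% re-measured, 86–87% at 50% and 93% at 75%. So the main damage is to the size and interpretation of the estimate. The bias from unequal visiting is conditional, as nothing in the SAP shows that visiting will differ.

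Finally, the year is plainly a typing slip and adds nothing to the weight of the main point.

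**Conclusion.** The point holds. As written, H3 admits pre-start readings as follow-up outcomes, and the printed 3- and 6-month dates are wrong in both lists. Both follow from the text without any assumption, as does the direction of the dilution when the groups are re-measured equally often and visits do not depend on pressure.

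The sizes are illustrative. Across the visit rates tried, an assumed −5 mmHg would be reported as −1.0 to −2.1 at 1 month, −2.4 to −4.0 at 3 months and −3.4 to −4.7 at 6 months. The problem is therefore greatest at 1 month, where a null H3 result could not be told apart from few patients having been re-measured. This should be fixed, but it does not invalidate the plan. It does not establish which version of the outcome should lead.

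**What to change.** - Correct the dates in both lists to 2/18/2021 and 5/18/2021. For H2 this is the only change.
- Add to H3 an analysis of the latest face-to-face office reading after 11/19/2020 and on or before each measure date. Day 0 itself belongs to the baseline matching window. Report it beside the latest-available version, treating neither as reliable alone.
- Report the number and percentage with a post-start reading, by group and date, and interpret H3 in that light, especially at 1 month.
- Recheck balance on the matching variables among patients with a post-start reading.
- In the RPM-enrolled comparison, apply the same bound from the index date, and state whether that is enrollment (as in the follow-up sentence) or RPM ordering (as in the matching sentence).

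The cost is wording and code, with no new data. The added analysis has fewer patients, may be biased if visits depend on pressure or on RPM, and breaks matched sets. The SAP plans to "attempt to match pilot to control at rate of 4:1 for primary and 2:1 for secondary". Read this as k controls per pilot patient, and assume that members of a set share a visit category and visit independently with probability p. Then the share of sets fully intact is mean p^(k+1), and the share of re-measured pilot patients who keep at least one re-measured control is mean p(1 − (1 − p)^k) divided by mean p. Over the first two rate mixes:

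| | 1 month | 3 months | 6 months |
|---|---|---|---|
| 4:1 sets fully intact | under 1% | 7–9% | 28–37% |
| At least one control kept, 4:1 | 65–69% | 92–96% | 98–99% |
| At least one control kept, 2:1 | 42–45% | 77–82% | 90–95% |

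Hence the balance recheck and the two versions side by side.

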We will retrospectively, at the end of the study end date, identify matched controls (4:1) for patients enrolled in RPM selected from patients in the non-pilot clinics and matched on the same baseline criteria (assessed at the time of RPM ordering). We will perform comparisons analogous to those described above for the primary cohort.

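### Controls are matched on sex, age, prior SBP and visit category, but H1 adjusts for none of these and H2 and H3 only for baseline SBP

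*SAP*

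**What the plan says.** The opening list of the SAP plans a matched control cohort and says the study will "attempt to match pilot to control at rate of 4:1 for primary and 2:1 for secondary". Under Matching criteria the factors are sex, age within 5 years, mean SBP in each half of the preceding year (each within 10 mm Hg), and primary care office visits in the past year in four categories.

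Under Hypothesis testing, the terms of each model are named:

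- H1 (number of medication intensifications): Poisson if the variance is close to the mean, "otherwise negative binomial regression with study group as the independent variable". There is no covariate.
- H2 (NQF 0018 satisfied): "using logistic regression with study group and baseline systolic blood pressure as independent variables".
- H3 (SBP at the latest face-to-face office visit): compared "among patients in the study group and control group using linear regression with study group and baseline systolic blood pressure as independent variables".

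Under RPM enrolled patient analyses, the SAP will "identify matched controls (4:1) for patients enrolled in RPM selected from patients in the non-pilot clinics" on the same baseline criteria and run analogous comparisons. No conditional or stratified model, set-level random effect, GEE or set-clustered standard error is mentioned for any of these analyses. There is also no rule for pilot patients who receive fewer controls than planned.

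**The concern.** The design uses five matching factors and the models use at most one quantity related to them. Age, sex and visit category enter no model. Two consequences follow.

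First, if the matching factors predict the outcome beyond what the model contains, patients in the same set have positively correlated outcomes. An ordinary regression treats them as unrelated and reports a standard error for the group difference that is larger than the true one.

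Second, matching balances the pooled groups on the matching factors only if each pilot patient contributes the same number of controls. The SAP promises only an attempt. If patients who are hard to match receive fewer controls, the control group under-represents their type. H2 and H3 can correct the part carried by baseline SBP; H1 can correct nothing.

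At stake are some precision in all three comparisons and, if set sizes vary, a possible distortion of the estimate, with H1 the least protected.

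**Working it through.** **Inputs.** Ratios, matching factors and model terms are from the SAP. The ratio is read as controls per pilot patient. The SAP gives no sample size, alpha, power, effect size or within-set correlation, so there is no stated figure to reproduce. Values of rho, two-sided alpha 0.05 and 100 sets are assumptions for illustration.

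**Standard error, fixed ratio 1:k, n sets, outcome variance s².**

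- Variance of the pilot mean: s²/n.
- Variance of the control mean: (s²/n) × (1 + (k - 1)rho)/k.
- Covariance of the two means: rho × s²/n.
- True variance of the difference: (s²/n) × [1 + (1 + (k - 1)rho)/k - 2rho] = (s²/n)(1 + 1/k)(1 - rho).
- Variance assumed by the unmatched model: (s²/n)(1 + 1/k).

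So reported SE / true SE = 1/sqrt(1 - rho), whatever k is. The actual two-sided type I error is 2 × (1 - Phi(1.96/sqrt(1 - rho))). If the matched analysis has 80% power, the unmatched one has Phi(0.84 + 1.96 - 1.96/sqrt(1 - rho)).

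| Assumed rho | SE ratio | Type I error | Power against 80% |
|---|---|---|---|
| 0.02 | 1.010 | 0.048 | 79.4% |
| 0.05 | 1.026 | 0.044 | 78.5% |
| 0.10 | 1.054 | 0.039 | 76.9% |
| 0.20 | 1.118 | 0.028 | 72.9% |

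**Simulation under the null, 100 sets.**

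- Linear model with baseline SBP, rho 0.10: mean model-based SE 0.112 against an empirical 0.104 for k = 4 (rejection 3.2%), and 0.122 against 0.113 for k = 2 (3.4%).
- Same model, rho 0.05: the difference was within simulation error.
- Set-clustered SEs, all linear runs including rho 0.30: rejection 4.7% to 5.8%.
- Negative binomial and logistic models without covariates, strong shared set effect (SD 0.8 on the link scale): 2.3% to 3.1% unclustered and 3.7% to 5.5% clustered.
- Same models, SD 0.4: 2.1% and 3.7% unclustered for counts, 4.3% and 5.2% for the logistic model.

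**Is H1 the worst case for the standard error?** For a count with mean mu and shared log-rate SD s, rho = mu(e^(s²) - 1)/(1 + mu(e^(s²) - 1)). With assumed mu = 0.3 and s = 0.3, mu(e^0.09 - 1) = 0.0283, rho = 0.0283/1.0283 = 0.027, and the SE ratio is 1.014. Count noise dilutes the correlation, so having no covariates does not by itself make the SE error large.

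**Unequal set sizes (assumed figures, no true effect).** Half the pilot patients are of a type with mean 0.6 intensifications, half of a type with mean 0.3.

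- Pilot mean: (0.6 + 0.3)/2 = 0.45.
- First type gets 2 controls each, second gets 4: control mean (2 × 0.6 + 4 × 0.3)/6 = 0.40, so the rate ratio is 0.45/0.40 = 1.125.
- Reversed, 4 and 2: control mean (4 × 0.6 + 2 × 0.3)/6 = 0.50, so the rate ratio is 0.45/0.50 = 0.90.

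The distortion can go either way, and H1 as written would report it as an effect of RPM.

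**The case against.** The strongest reply is that an unmatched, covariate-adjusted analysis of a matched cohort is a defensible choice. With a fixed ratio, matching already removes confounding by the matching factors, and the remaining SE error does not create false positives. In H2 and H3, baseline SBP is the covariate closest to the outcome. Residual rho then cannot much exceed the share of outcome variance explained by sex, age within a 65-to-85 range (primary population), visit category and leftover SBP history. Nothing in the SAP suggests that this share reaches 10%. Matching here plausibly serves comparability between clinics, and the SAP claims no precision aim for it.

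Most of this stands. It limits the SE effect to a few percent at plausible values, and it rules out two stronger readings. A reader might infer that ignoring the matching makes the tests anti-conservative; with positive within-set correlation and a fixed ratio the opposite holds. A reader might also infer that H1 suffers the largest SE error because it has no covariates; the count calculation shows that this does not follow.

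What does not stand is the reliance on a fixed ratio. The SAP only attempts one and gives no rule for incomplete sets. Under variable set sizes neither the balance argument nor the 1/sqrt(1 - rho) formula holds as stated. Nor is this a matter left to a protocol, since the SAP itself lists the terms of each model.

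**Conclusion.** The point holds as a minor one. The SAP matches on factors that its models mostly omit, and it names no matched-set term. With a fixed ratio, the cost is standard errors about 1% to 5% too large for an assumed residual rho of 0.02 to 0.10, or roughly 0.6 to 3 percentage points of power from 80%. With unequal sets there is also a possible imbalance in the pooled controls, which H1 cannot correct. Its size cannot be estimated from the SAP, and the 1.125 and 0.90 above show only the mechanism.

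The SAP does not support calling the planned results invalid or the loss of power large: it gives no rho, sample size or power target against which to show either. Clinic-level clustering is a different matter. It can make standard errors too small, so the conservative direction found here should not be read as a statement about the analysis as a whole.

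**What to change.** In H1, H2 and H3, and in the analogous RPM-enrolled comparison, include the matching variables as covariates: age, sex, visit category and the two prior SBP means, alongside the baseline SBP already planned for H2 and H3. State how incomplete sets are handled and whether a control may be reused.

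Standard errors clustered on the matched set can be named as an alternative or sensitivity analysis. They add little once all matching variables are in the model, and on their own they do not correct imbalance from unequal set sizes, so the covariates should be the main change.

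The cost is small, because the values must already be held to carry out the matching. The covariates add seven coefficients (age 1, sex 1, visit category 3, SBP means 2), which could matter if 1-month counts are sparse; the SAP gives no sample size to judge this. The H2 odds ratio becomes conditional on more covariates, which should be stated when it is reported. Clinic-level clustering needs its own provision. Matched sets cross clinics, so handling both kinds of clustering together would take more than a single software option.

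### H2 and H3 adjust for one undefined baseline systolic pressure; the natural reading, a single visit value, uses less than the plan already extracts and can mislead in the RPM-enrolled comparison

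*SAP*

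**What the plan says.** Under Hypothesis testing, H3 compares systolic pressure at 1, 3 and 6 months "using linear regression with study group and baseline systolic blood pressure as independent variables". H2 compares the proportion meeting the blood pressure measure "using logistic regression with study group and baseline systolic blood pressure as independent variables". Neither says which pre-start value the covariate is.

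The SAP holds two kinds of pre-start systolic pressure:

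- **Last reading.** The list of quantities described at time 0 and at each follow-up includes "The systolic blood pressure at the most recent face-to-face office visit". This is also the H3 outcome.
- **Half-year means.** The Matching criteria use "Mean SBP from T-365d to T-183d (+/- 10 mm Hg" and "Mean SBP from T-182d to T-0d (+/- 10 mm Hg".

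The RPM enrolled patient analyses select controls "matched on the same baseline criteria (assessed at the time of RPM ordering", so there the word baseline is attached to the matching variables. The section then adds: "We will perform comparisons analogous to those described above for the primary cohort".

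**The concern.** This is the only adjustment covariate in two of the three hypothesis models. Those models are fitted at three time points, in two populations, and again for RPM enrollees. The estimate and its standard error depend on which value is used, and the SAP leaves that open.

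The time-0 value of the outcome is the obvious candidate for H3. It is a single office reading and carries full visit-to-visit noise, although means of several readings will already have been extracted for matching.

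The RPM-enrolled comparison has a further problem. Matching aligns the groups on the half-year means, but nothing aligns them on the last reading. If a high last reading prompts the order, enrollees and controls with similar usual pressure will differ on that reading. A model holding only the last reading expects enrollees to stay higher. When they return to their usual level, it credits the fall to RPM.

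**Working it through.** The SAP gives no standard deviation, sample size or effect, so there is no figure of its own to reproduce. The variance components, readings per window, carried-forward shares and ordering rules below are assumptions.

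Write R for the last reading, and M1 and M2 for the earlier and later half-year means.

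**1. Precision when every outcome is a new reading.** In the stable case, take a between-person SD of 10 and a visit-to-visit SD of 10 mm Hg (total about 14). The residual variance of a new reading given k earlier readings is 100 + 100/(1 + k).

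- R alone (k = 1): 100 + 50 = 150.
- R, M1 and M2, one reading per window (k = 2): 100 + 33.3 = 133.3. Ratio 150/133.3 = 1.125.
- R, M1 and M2, two plus two readings (k = 4): 100 + 20 = 120. Ratio 150/120 = 1.25.
- R, M1 and M2, two plus three readings (k = 5): 100 + 16.7 = 116.7. Ratio 150/116.7 = 1.29.

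So R alone inflates residual variance by 12.5-29%. The standard error is larger by √1.125 = 1.06 to √1.29 = 1.13.

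With drift over time in a person's usual pressure (person/drift/visit SDs), the inflation over the three-covariate model is:

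| Pressure pattern | R alone | M1 + M2 |
|---|---|---|
| Stable, 10/0/10 | 12.5-29% | 0% |
| Mild drift, 9/5/9.5 | 8.5-19% | at most 0.2% |
| Strong drift, 6/9/8 | 2-5% | at most 1.2% |

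M2 alone loses 2-12.5% across these cases.

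**2. Precision when some outcomes are the unchanged baseline reading.** The outcome is the most recent visit, and the SAP does not require a visit after time 0. Let p be the share carried forward, v the residual variance of a new reading, and d the variance of R minus its predicted new value. The residual variance is then (1 − p)v + p(1 − p)d. For the stable case with two plus two readings and p = 0.5:

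- R alone (v = 150, d = 50): 75 + 12.5 = 87.5.
- R, M1 and M2 (v = 120, d = 80): 60 + 20 = 80.
- Ratio 87.5/80 = 1.094. The 400,000-patient simulation gave 9.5%.

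Simulated inflation over the three patterns:

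| Share carried forward | R alone | M1 + M2 |
|---|---|---|
| 50% | 2-10% | 16-18% |
| 80% | 1-3% | 85-88% |

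**3. RPM-enrolled comparison, true effect zero.** The simulation used 150 enrollees, 4:1 matching within 10 mm Hg on M1 and M2, and 50 runs per setting (Monte Carlo error about 0.10-0.17 mm Hg). With ordering on the last reading and more than one reading in the recent window, enrollees' R was about 7-10 mm Hg above that of matched controls.

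The adjusted coefficient equals the unadjusted difference minus the slope times that gap. In one strong-drift setting (two plus two readings, new outcomes) the unadjusted difference was +1.66 and the gap 8.7. The coefficient was -0.93, so the slope is (1.66 + 0.93)/8.7 = 0.30.

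Results adjusting for R alone (negative favours RPM):

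| Ordering and outcomes | Null estimate, mm Hg |
|---|---|
| On last reading, stable, new outcomes | -1.6 to -2.7 |
| On last reading, stable, 50% carried forward | -0.8 to -1.3 |
| On last reading, strong drift, new outcomes | -0.5 to -0.9 |
| On last reading, strong drift, 50% carried forward | -0.2 to -0.6 |
| On last reading, one reading per window (R = M2) | -0.5 to +0.2 |
| At random | -0.2 to +0.3 |
| On the sustained mean | 0 to +0.9 |

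The first four rows use two plus two or two plus three readings. In those settings M1 + M2 without R gave +2.3 to +4.8 mm Hg, against RPM, at 50% carried forward. With all three covariates the null estimate stayed between -0.4 and +0.3 mm Hg in every ordering scenario. With ordering on the last reading and new outcomes, its standard error was about 0-7% above that of M1 + M2.

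**The case against.** The strongest reply is that H3 analyses a variable the SAP also describes at time 0, so its baseline is ordinarily that time-0 value. The SAP uses the means only for matching. On that view this is at most a clarification, and a less efficient covariate is not an error. The first part is fair and is taken here as the natural reading. It does not remove the point, because that reading is the one with the precision loss and the RPM-enrolled risk.

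Two stronger conclusions might be inferred, and neither is supported.

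- **That any single choice of baseline loses precision.** The two half-year means together lose at most 1.2% when outcomes are new readings. They lose materially only when many outcomes are carried forward.
- **That the last reading does bias the RPM-enrolled comparison towards RPM.** This needs ordering in reaction to a high last reading and more than one reading in the recent window. The SAP states neither, and what prompts an order may be set out in the protocol. A separate simulation with 200 patients, ordering at a last reading of at least 140 or 150, gave -0.6 to -1.5 mm Hg (standard error 1.0-1.2). This shrank to about -0.15 to -0.4 when both groups had to meet the rule of two elevated readings.

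Three further limits stand. The primary-cohort rule can be met on diastolic pressure, so systolic pressure is not strictly truncated there. The SAP presents the RPM-enrolled work as exploratory. The matching categories include patients with one primary care office visit in the year, and one visit cannot supply a reading in both windows.

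**Conclusion.** The concern holds in a limited form. The covariate in H2 and H3 is undefined. Under its natural reading, H3 gives up about 2-29% in residual variance when outcomes are new readings, and about 1-10% when 50-80% are carried forward. In the RPM-enrolled comparison there is a conditional risk of a spurious difference of roughly 0 to -3 mm Hg favouring RPM. With random ordering the error is about nil, and with ordering on the sustained mean it is nil or against RPM.

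Using only the half-year means is not a safe substitute, because it can fail in the other direction when outcomes are carried forward. The three-covariate model was never materially worse in the main comparison, and it stayed near zero in every ordering scenario tested.

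These sizes depend on the assumed variance components and were computed for the linear model. No size was computed for H2, although its odds ratio is also conditional on whichever baseline is entered. This should be settled before analysis; it does not invalidate the design.

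**What to change.** In H2, H3 and the analogous RPM-enrolled models, replace the single undefined covariate with three:

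- systolic pressure at the last face-to-face office visit on or before T-0;
- the later half-year mean used for matching;
- the earlier half-year mean used for matching.

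For the RPM-enrolled comparison, take all three at the RPM order date, and at the corresponding index date for controls.

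State a rule for patients with no reading in one window, for example a missing-window indicator, so that they are not dropped.

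The cost is one sentence, two model terms, the missing-window rule, and a slightly larger standard error in some RPM-enrolled scenarios. The values are already needed for matching and for the time-0 description. Whether an unchanged baseline reading should count as an outcome is a separate question that this change does not settle.
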